## 6.2 Definition of Dose-Limiting Toxicity

Toxicity will be assessed using the NCI's CTCAE version 5.0. A DLT is defined as an AE or abnormal laboratory value assessed as being at least possibly related to the study medication, which occurs within 60 days after the second cycle of Sn-117m-DTPA.

A DLT is defined as:

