### 9. STATISTICAL CONSIDERATIONS

#### 9.1 Study Design/Endpoints

This is a single-arm, open-label phase 2 study to evaluate the efficacy of Sn-117m-DTPA on

sustained pain response in patients with CRPC metastatic to at least two bone sites, with at least one clinically meaningful pain at baseline ( $\geq 4$  on an 11-point pain intensity scale). Sustained pain-response is defined as: 1) achieving pain index  $\leq 3$  within a 12-week period and 2) maintaining that pain index  $\leq 3$  over a 16-week time period (beginning when the pain index  $\leq 3$  is initially achieved). The maximum duration of follow-up required to declare a patient a responder is 28 weeks, representing a patient who initially achieves pain index  $\leq 3$  toward the end of the 12-week period and is followed for an additional 16 weeks to confirm maintenance of pain index  $\leq 3$ .

Eligible patients will be assigned to receive Sn-117m-DTPA at 20 mCi/70 kg (0.28 mCi/kg) every 8 weeks for two cycles. Treatment will last for 16 weeks with two treatment injections given at 8-week intervals. The study utilizes a mini-max Simon two-stage design to assess anti-tumor activity and pain benefit of Sn-117m-DTPA.

Patients are not allowed to receive external radiation within 12 weeks from the start of treatment administration. If their pain index does not reach  $\leq 3$  after 12 weeks, they are not meeting the primary endpoint, and they can then get external radiation for pain control.

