The sustained pain response rate under null hypothesis is  $p_0=0.1$  and the alternative hypothesis is  $p_1=0.3$ . The literature on sustained pain-relieving benefit with radiopharmaceutical drugs in prostate cancer with bone metastases is limited. Nilsson *et al.* studied the dose-response relationship and pain-relieving effect of radium-223 (Nilsson *et al.*, 2012). Pain response at Week 8 was seen in 40% of patients. The null hypothesis for sustained pain response in the absence of effective therapy and a strong literature support would assume 10%. We propose that the sustained pain response with Sn-117mDTPA would achieve 30%. Using the mini-max Simon's two-stage design, the total sample size is 25 patients, with 10 patients for the first stage and 15 patients for the second stage. If 1 or 0 patients achieve sustained pain response in the first stage, the study will be stopped early for futility; otherwise the trial continues to the second stage. If 5 or fewer patients achieve sustained pain-response, then no further investigation of the study treatment is warranted. This design has an estimated 5% type I error rate and 80% power. The planned sample size and interim analysis has a 3.28% actual type I error rate and 80.17% actual power. The probability of stopping at the end of the first stage is about 55% under the null hypothesis. Study enrollment will be interrupted for the interim efficacy analysis.

The efficacy primary endpoint will also be summarized by the point estimation of the ORR with the corresponding 95% confidence intervals. Patients who received any amount of study drug will be included in the denominator for the calculation of ORR.

Summary statistics on safety endpoints will be calculated and reviewed at the interim analysis or anytime during the study at the investigator's discretion. If there is statistically significant evidence that the DLT probability exceeds 30%, the study should be suspended for further review. A 95% exact binomial confidence interval will be calculated for the DLT rate. If the observed lower bound of the confidence interval exceeds 30%, we consider it statistically significant evidence that the DLT probability exceeds 30%.

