## 9.2 Sample Size/Accrual Rate

The total sample size is 25 patients, with 10 patients for the first stage and 15 patients for the second stage. An interim analysis for efficacy will be conducted after the first 10 patients have become evaluable for the primary endpoints. Study enrollment will be interrupted for the interim analysis. Patients will be accrued at an anticipated rate of 1-2 patients per month.

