## Stopping Criteria

Stopping criteria will be applied if 1) there is evidence of treatment related AEs or 2) lack of efficacy.

- 1) We will review safety data at interim analysis or at any point if there are reasons for concern about safety. If there is strong evidence that the DLT rate is unacceptably high (>30%), we will suspend the study.
- 2) An interim analysis for efficacy will be conducted after the first 10 patients have become evaluable. If 1 or 0 patients achieve the primary endpoint, then the study will be stopped early for futility.

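### The 30% DLT suspension rule has one scheduled test, at the efficacy interim, with about 17% power against a 50% DLT rate; later protection rests on looks with no stated time or boundary

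*Combined protocol and SAP*

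**What the plan says.** Section 9.1 holds the only numeric safety stop: "A 95% exact binomial confidence interval will be calculated for the DLT rate", and "If the observed lower bound of the confidence interval exceeds 30%, we consider it statistically significant evidence that the DLT probability exceeds 30" per cent. Stopping Criteria repeats the intent: "If there is strong evidence that the DLT rate is unacceptably high (>30%), we will suspend the study".

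On timing, Section 9.1 says "Summary statistics on safety endpoints will be calculated and reviewed at the interim analysis or anytime during the study at the investigator's discretion", and Stopping Criteria says "We will review safety data at interim analysis or at any point if there are reasons for concern about safety". The interim itself is fixed by efficacy data in Section 9.2: "An interim analysis for efficacy will be conducted after the first 10 patients have become evaluable for the primary endpoints". Section 9.1 adds that "The maximum duration of follow-up required to declare a patient a responder is 28 weeks".

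Section 6.2 counts a DLT as an event "which occurs within 60 days after the second cycle of Sn-117m-DTPA". Section 9.6.1 bases safety analyses on everyone who received at least one dose. The plan gives no table of DLT boundaries, no timing or trigger for the unscheduled looks, and no operating characteristics for the rule.

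**The concern.** A numeric suspension rule protects patients only when someone applies it. Here the one guaranteed application waits for an efficacy endpoint, uses few patients, and is not repeated in the second stage. A drug with a DLT rate well above the sponsor's limit would usually pass that test. After it, suspension depends on someone becoming concerned enough to run the calculation, which is the judgement a prespecified rule is meant to support. Looks prompted by concern also leave the rule's error rates undefined.

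**Working it through.** **Inputs.** Limit 30% and exact 95% interval (9.1). Interim at 10 evaluable patients, 25 in total, accrual 1-2 per month (9.2). Response confirmed within at most 28 weeks (9.1). DLT window of 60 days after the second cycle (6.2). True DLT rates of 30% to 70% are scenarios; the documents give only the 30% limit.

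**1. The plan's own figures.** None is given for the DLT rule, but the size of the interim can be checked against the stated type I error (3.28%), power (80.17%) and early stopping (about 55%), with cut-offs of 1 and 5.
- Stages 10 + 15: early stopping under the null = 0.9^10 + 10 × 0.1 × 0.9^9 = 0.349 + 0.387 = 73.6%; type I error 2.77%; power 74.0%. These do not match.
- Stages 15 + 10: 0.9^15 + 15 × 0.1 × 0.9^14 = 0.206 + 0.343 = 54.9%; type I error 3.28%; power 80.17%. These match.

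The printed stage sizes look transposed, so both 10 and 15 are carried forward.

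**2. Boundary.** The two-sided exact lower limit for x DLTs in n patients is the 2.5% quantile of Beta(x, n − x + 1).
- n = 10: 6/10 gives 26.2%, 7/10 gives 34.8%. Seven are needed.
- n = 15: 8/15 gives 26.6%, 9/15 gives 32.3%. Nine are needed.
- A one-sided 95% limit at n = 10: 6/10 gives 30.35%. Six would do.

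**3. Power of the scheduled look at a true 50%.**
- n = 10: (120 + 45 + 10 + 1)/1024 = 17.2%.
- n = 15: 9949/32768 = 30.4%.
- n = 10, one-sided: 37.7%.

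At true rates of 30%, 40%, 60% and 70%, the two-sided look at n = 10 triggers with probability 1.1%, 5.5%, 38.2% and 65.0%.

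**4. Timing.** Ten patients take 5-10 months to accrue, and the last may need up to 28 weeks (6.4 months), so the first scheduled test falls at about months 11-16. If accrual pauses only for the analysis, 6.4 × 1 to 6.4 × 2, or about 6-13, further patients could be dosed first.

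**5. Scheduled looks at 5, 10, 15 and 20.** The boundaries are 5/5, 7/10, 9/15 and 11/20. An exact recursion gives the probability of first crossing at each look:

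| True rate | 5 | 10 | 15 | 20 | Total | Adding 13/25 |
|---|---|---|---|---|---|---|
| 30% | 0.0024 | 0.0095 | 0.0095 | 0.0078 | 2.9% | 3.5% |
| 40% | 0.0102 | 0.0480 | 0.0545 | 0.0505 | 16.3% | 20.8% |
| 50% | 0.0313 | 0.1465 | 0.1525 | 0.1281 | 45.8% | 56.1% |
| 60% | 0.0778 | 0.3113 | 0.2431 | 0.1512 | 78.3% | 87.3% |
| 70% | 0.1681 | 0.4867 | 0.2238 | 0.0803 | 95.9% | 98.6% |

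Mean patients treated at a true 50%:
- one look at 10: 25 − 15 × 0.1719 = 22.4;
- four looks: 25 − 20 × 0.0313 − 15 × 0.1465 − 10 × 0.1525 − 5 × 0.1281 = 20.0.

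Both means ignore futility stopping and assume that no one is dosed while a look is pending.

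**The case against.** The strongest reply is that looks are allowed at any time. A reader might infer that a trial with a 50% DLT rate would be suspended only 17% of the time. The documents do not support that: 17% belongs to one look. Sections 9.1 and Stopping Criteria permit others, and the suspension sentence is not confined to the interim. If the bound were checked after every patient through 25, the probability would be about 61%. What stands is that the plan does not say where between 17% and 61% the trial would fall.

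Nor are 17% and 61% like for like. Checking after every patient gives only 22.7% by patient 10, and looks at just 10 and 25 give 52.0%. Most of the gain comes from testing second-stage patients, not from testing more often in the first stage.

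The denominator at the interim need not be 10, because safety analyses include everyone dosed. With 16, 20 or 23 patients assessable, the rule needs 10, 11 or 12 DLTs and has 22.7%, 41.2% or 50.0% power at a true 50%. That is better, but only because more patients have been treated before the first scheduled test.

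The delay should not be overstated. Twenty-eight weeks is a maximum, and failure to respond can be known at week 12. The DLT window closes near week 17 if counted from the second injection, or near week 25 if counted from the end of cycle 2. Complete DLT data therefore precede the 28-week maximum by about 11 or 3 weeks.

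Other safeguards are real: ongoing review by the principal investigator and institutional monitoring plans (13.1), monthly reports to drug monitors (13.2.2), expedited reporting of grade 3 or higher marrow and renal or genitourinary events (10.3.4), and an end to the individual's treatment after a DLT (6.4). None of them requires the interval rule to be applied.

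**Conclusion.** The concern holds in this form: the rule has one scheduled application, tied to efficacy, with about 17% power at a true 50% DLT rate (about 30% if the first stage is 15). Stage 2 has no scheduled test. The remaining protection has no stated time or boundary.

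The 17% rests on a two-sided interval, exactly 10 patients with known DLT status, and a single look. The 50% rate is a scenario, not a prediction. No figure here is the overall suspension probability of the trial, which the documents do not allow anyone to compute. Scheduled looks would give a material gain for a small increase in unnecessary pauses, so this is more than a missing detail.

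**What to change.** Keep the 30% limit and the two-sided exact 95% lower bound. Schedule the test independently of the efficacy interim, in both stages: when the first 5, 10, 15 and 20 treated patients, in order of entry, have each completed the DLT window or had a DLT. Print the boundary in 9.1 and Stopping Criteria: 5/5, 7/10, 9/15, 11/20, and 13/25 at the end. Keep the discretionary looks.

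Patients with and without a DLT should enter the denominator on the same basis. Testing whenever a DLT occurs, while counting other patients only once their window closes, inflates the running rate. In simulation (even accrual of 1-2 per month, a 17- or 25-week window, onset uniform over the window or at weeks 4-8), that gave suspension at a true 30% in about 8-37% of trials, against 5.6% when status is known in order of entry.

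Also state:
- whether the interval is two-sided;
- the DLT denominator, including how a patient with no second injection is counted, and the start of the 60 days;
- whether accrual continues while a look is pending;
- stage sizes that agree with the stated type I error, power and early-stopping figures.

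The cost is protocol wording and a running DLT tally from data already collected in Rave. Suspension for review at a true 30% rises by 1.9 points to 2.9% (3.5% with the final look).

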## 9.2 Sample Size/Accrual Rate

The total sample size is 25 patients, with 10 patients for the first stage and 15 patients for the second stage. An interim analysis for efficacy will be conducted after the first 10 patients have become evaluable for the primary endpoints. Study enrollment will be interrupted for the interim analysis. Patients will be accrued at an anticipated rate of 1-2 patients per month.

## PLANNED ENROLLMENT REPORT

Racial Categories	DOMESTIC PLANNED ENROLLMENT REPORT (TREATMENT)				Total	
	Ethnic Categories					
	Female	Male	Female	Male		
American Indian/ Alaska Native	0	0	0	0	0	
Asian	0	0	0	0	0	
Native Hawaiian or Other Pacific Islander	0	0	0	0	0	
Black or African American	0	3	0	0	3	
White	0	22	0	0	22	
More Than One Race	0	0	0	0	0	
Total	0	25	0	0	25	

PHS 398 / PHS 2590 (Rev. 03/20 Approved Through 2/28/2023)

OMB No. 0925-0001/0002

## Stopping Criteria

Stopping criteria will be applied if 1) there is evidence of treatment related AEs or 2) lack of efficacy.

- 1) We will review safety data at interim analysis or at any point if there are reasons for concern about safety. If there is strong evidence that the DLT rate is unacceptably high (>30%), we will suspend the study.
- 2) An interim analysis for efficacy will be conducted after the first 10 patients have become evaluable. If 1 or 0 patients achieve the primary endpoint, then the study will be stopped early for futility.

## 9.3 Stratification Factors

This is a single-arm phase 2 study with no stratification factors.

## 9.4 Analysis of Secondary Endpoints

Secondary endpoints will be summarized depending on data type. Categorical endpoints will be summarized by frequency and percent. Continuous variables will be summarized by mean and standard deviation at each assessment time point. Time-to-event endpoints will be summarized by Kaplan-Meier Methods. Safety and toxicity will be assessed through the frequency and percent of adverse events (AEs), serious adverse events (SAEs), and adverse events of special interests (AESIs). Toxicity will be assessed using Common Terminology Criteria for Adverse

Events v 5.0 (CTCAE). Safety and toxicity will also be assessed by patient-reported outcomes and adverse events (PRO-CTCAE) captured by digital instruments during treatment and 8 weeks after the last injection to monitor for acute toxicity and every 2-4 weeks for 6 months post-therapy for monitoring of long-term toxicity. CTCAE grades for the corresponding time period will be presented in conjunction with PRO-CTCAE scores. PSA and ALP response rates will be calculated for each of the above defined categories with the corresponding confidence intervals. *Post-hoc* analysis on PSA and ALP levels may be conducted to explore possible trends in PSA and ALP levels. Time to the first symptomatic skeletal event will be analyzed using the Kaplan-Meier method. Estimation and confidence intervals for the median time to first symptomatic skeletal event will be provided. Patients who did not have a symptomatic skeletal event will be censored at the last study visit. PFS will be analyzed in a similar manner as the time to first skeletal event. Patients who did not have observed clinical progression will be censored at the last assessment.

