**Patient Cloud**

#### **4.4 General Guidelines**

Following registration, patients should begin protocol treatment within 30 days. Issues that would cause treatment delays should be discussed with the Principal Investigator. If a patient does not receive protocol therapy following registration, the patient's registration on the study may be canceled. The Study Coordinator should be notified of cancellations as soon as possible.

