#### 9.4.3 Time to First Symptomatic Skeletal Event

The time from study enrollment to 1) the first use of external-beam radiation therapy to relieve skeletal symptoms, 2) new symptomatic pathologic vertebral or non-vertebral bone fractures, 3) spinal cord compression, or 4) tumor-related orthopedic surgical intervention will be evaluated.

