#### 9.4.9 Overall Survival

OS will be calculated from the time of the first study treatment until the date of death. OS data will be censored if death is not observed.

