### **9.6.2 Evaluation of Response**

The Per Protocol Population is defined as all patients who are in the Safety Population and have no major protocol violations that could influence the assessment of efficacy. Efficacy analysis, including the analysis of primary and secondary endpoints (excluding safety and toxicity), will be based on the Per Protocol Population.

Responses to treatment will be evaluated per PCWG3 criteria as described in Section 12.1 (for bone lesions).

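### Time to first symptomatic skeletal event: deaths without an event are censored, so one minus Kaplan-Meier is not actual risk, and the clock starts up to 30 days before first dose; the two effects oppose each other

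*Combined protocol and SAP*

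**What the plan says.** **Estimator and censoring.** Section 9.4 states: "Time to the first symptomatic skeletal event will be analyzed using the Kaplan-Meier method". It promises a median with confidence interval and adds: "Patients who did not have a symptomatic skeletal event will be censored at the last study visit".

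**Endpoint.** Section 9.4.3 defines it as "The time from study enrollment to 1) the first use of external-beam radiation therapy to relieve skeletal symptoms", then symptomatic pathologic fracture, then "3) spinal cord compression, or 4) tumor-related orthopedic surgical intervention will be evaluated". Death is not a component there or in objective 1.2.4. No competing-risk method appears for this endpoint.

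**Analysis set.** Section 9.6.2: "Efficacy analysis, including the analysis of primary and secondary endpoints (excluding safety and toxicity), will be based on the Per Protocol Population". That population is "all patients who are in the Safety Population and have no major protocol violations" that could affect the efficacy assessment. Section 9.6.1 defines the Safety Population by receipt of at least one dose.

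**Gap to first dose.** Section 4.4: "Following registration, patients should begin protocol treatment within 30 days". Section 11 repeats the 30-day limit as a requirement.

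**Other clocks.** Section 9.4.9: "OS will be calculated from the time of the first study treatment until the date of death". Section 12.2.6 starts PFS at the start of treatment, whereas Section 9.4.8 starts clinical PFS at enrolment. Section 6.5 counts the 12-month follow-up from first dose and ends it earlier only at death. Section 11 footnote a also names disease progression as an end of follow-up visits.

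**The concern.** There are two separate faults.

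1. A patient who has died cannot have a later skeletal event. Kaplan-Meier with that death censored treats him as still able to have one. The curve then answers what would happen if nobody died, and its complement is larger than the proportion of patients who actually have an event. The promised median is affected in the same way.

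2. The clock starts before treatment in patients who are selected because they were later treated. Survival through the gap is guaranteed by the analysis set, and the gap is added to each patient's time. A skeletal event inside the gap would count as an event before any drug exposure.

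With no control arm, this result can only be read alone or against outside figures; Section 2.1.1 itself cites a median benefit for radium-223 on time to first symptomatic skeletal event. A reader could take the curve for absolute risk, on a time scale that differs from the trial's own OS and follow-up window.

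**Working it through.** **Plan's own figure.** None to reproduce: the documents state no event rate, death rate or precision for this endpoint. All rates below are assumptions.

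**Fault 1: competing deaths.** Let h be the monthly hazard of a skeletal event and d that of death without one, both constant.

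- One minus Kaplan-Meier: 1 − exp(−h·t)
- Cumulative incidence: h/(h+d) × [1 − exp(−(h+d)·t)]

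At t = 12 months:

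| h, d per month | 1 − KM | Cumulative incidence | Excess (points) |
|---|---|---|---|
| 3%, 3% | 1 − exp(−0.36) = 30.2% | 0.5 × [1 − exp(−0.72)] = 25.7% | 4.6 |
| 5%, 5% | 1 − exp(−0.60) = 45.1% | 0.5 × [1 − exp(−1.20)] = 34.9% | 10.2 |
| 8%, 7% | 1 − exp(−0.96) = 61.7% | 8/15 × [1 − exp(−1.80)] = 44.5% | 17.2 |

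Excesses are from unrounded values. The death hazards correspond to medians of ln 2/0.03 = 23 and ln 2/0.07 = 10 months.

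A second grid (skeletal-event median 6 to 18 months on the Kaplan-Meier scale, 12-month deaths 10% to 50%) gives an excess of 1.7 to 16.7 points. For a 9-month median (h = ln 2/9, d = −ln(1 − deaths)/12):

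| 12-month deaths | 1 − KM | Cumulative incidence | Excess (points) |
|---|---|---|---|
| 10% | 60.3% | 57.7% | 2.6 |
| 20% | 60.3% | 55.0% | 5.3 |
| 30% | 60.3% | 52.1% | 8.2 |
| 50% | 60.3% | 45.8% | 14.5 |

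At 30% deaths, the time at which half of the patients have had an event is 11.1 months, against a Kaplan-Meier median of 9.0.

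Censoring at the last visit instead of the date of death adds a little more. A simulation of 200,000 patients on an approximate visit schedule, read at 11.9 months, gave a one-minus-Kaplan-Meier value of 60.9% at 30% deaths. The closed form is 1 − 2^(−11.9/9) = 60.0%, and simulated cumulative incidence was 51.9%.

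**Fault 2: origin.** The maximum gap is 30/30.4375 = 0.99 month. Added to the true median from first dose, it is 16.4% of 6 months, 11.0% of 9, 8.2% of 12 and 5.5% of 18. If nobody has an event in the gap, the apparent 12-month risk at a 9-month median falls from 60.3% to 1 − exp(−(ln 2/9) × (12 − 0.99)) = 57.2%, or 3.1 points. With a 7-day gap it falls to 59.6%.

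**Direction.** Fault 1 raises apparent risk and fault 2 lowers it. At a 9-month median, the 3.1 points from a full 30-day gap exceed the 2.6 points from 10% deaths, but are smaller than the 5.3 points from 20% deaths.

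**The case against.** The strongest case against is that this changes little. The endpoint is one of nine secondary objectives, carries no hypothesis and does not touch the two-stage decision rule. With 25 patients and no censoring, a 45% estimate has a 95% margin of 1.96 × √(0.45 × 0.55/25) = 19.5 points, wider than the whole assumed bias. OS is reported separately, so mortality is not hidden. Kaplan-Meier with deaths censored is a conventional cause-specific summary and may be the scale that other reports use. All of this stands and limits the weight of the point. It does not make the curve an estimate of actual risk, and sampling error does not excuse a removable bias.

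Stronger readings that a reader might infer, and why they fail:

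- **That reported risk will be too high overall.** The faults oppose each other, and without rates or typical gaps no net direction follows.
- **That the gap is event-free.** Receiving a dose guarantees survival to dosing, not freedom from a skeletal event. The bar on external radiation in Section 9.1 runs from the start of treatment, so it does not cover the gap.
- **That the plan expressly censors deaths, or that deaths will be frequent.** Censoring follows from the general rule; death is not named. The 3-month life expectancy in Section 3.1.7 is an entry floor, not a death rate, and visceral metastases are excluded.
- **That the 5 to 17 points are a forecast.** Constant hazards are a simplification: external radiation is an event component that Section 9.1 bars for the first 12 weeks and then allows.

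One objection changes the remedy. If skeletal follow-up stops at progression while dates of death are still collected (Section 6.5), entering those later deaths as competing events would understate incidence.

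**Conclusion.** The point holds as two limited faults. Under the general rule, patients who die without a skeletal event are censored at the last visit, so one minus Kaplan-Meier and its median do not describe actual risk when deaths occur. The excess at 12 months is about 5 to 17 points under constant hazards of 3% to 8% (events) and 3% to 7% (deaths) per month, and 1.7 to 16.7 points on the second grid. The mechanism is certain; the size is assumed. Separately, the enrolment origin adds 0 to 30 pre-treatment days and disagrees with the analysis set, OS and the follow-up window. Kaplan-Meier remains valid as a cause-specific summary. The change is worth making because it is cheap, not because a conclusion of the trial depends on it.

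**What to change.** In Sections 9.4 and 9.4.3:

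1. Measure time to first symptomatic skeletal event from the first Sn-117m-DTPA dose.
2. Report Aalen-Johansen cumulative incidence with a confidence interval. Count death without a skeletal event as a competing event, at the date of death, only while the patient is still under skeletal-event follow-up.
3. Censor patients alive without an event at their last skeletal assessment.
4. Keep the Kaplan-Meier curve and median, labelled as the cause-specific summary, for comparison with other reports.
5. Reconcile Section 6.5 with Section 11 footnote a on whether follow-up ends at disease progression, since this decides which deaths count under item 2.

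Cost: a few lines of analysis text and standard code. First-dose dates, event dates and dates of death are already needed for the planned analyses. Item 5 is a consistency edit that should come before the analysis rule is fixed.
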